## Clinical Study Protocol SMOF-028-CP4

### Smoflipid® (lipid injectable emulsion)

---

- sterols in plasma including phytosterols ( $\beta$ -sitosterol, campesterol, stigmasterol, brassicasterol, ergosterol, cholesterol, desmosterol, lanosterol,  $\beta$ -sitostanol, lathosterol, squalene)
- d Trace elements (Ferritin, Zn, Se, Cu, Mn, Cr).
  - e Prescribed daily dose, actual daily dose, infusion rates of PN products; type and quantity of enteral nutrition products and oral food.
  - f Recording of AEs starts after signature of informed consent.
  - g In all patients genetic polymorphism of two desaturase encoding genes (FADS1 and FADS2) will be determined. Only one blood sample is required which can be taken any time during the treatment period.

**Clinical Study Protocol SMOF-028-CP4**  
**Smoflipid® (lipid injectable emulsion)**

---

### **3. List of Abbreviations**

ADR	Adverse drug reaction
AE	Adverse event
ALP	Alkaline phosphatase
ALT	Alanine aminotransferase
ASPEN	American Society for Parenteral and Enteral Nutrition
AST	Aspartate aminotransferase
BMI	Body mass index
CRA	Clinical Research Associate
CRF	Case report form
CRO	Contract Research Organization
CRP	C-reactive protein
CSP	Clinical Study Protocol
CSR	Clinical Study Report
CTCAE	Common Terminology Criteria for Adverse Events
DEHP	di-2-ethylhexyl phthalate
DSMB	Data Safety Monitoring Board
CFR	Code of Federal Regulations
eCRF	Electronic case report form
EFAD	Essential Fatty Acid Deficiency
FADS1/2	Fatty Acid Desaturase (Genes) 1 and 2
FDA	Food and Drug Administration (United States)
FDCA	United States Federal Food, Drug, and Cosmetics Act
GCP	Good Clinical Practice
GGT	Gamma-glutamyl transpeptidase
GMP	Good Manufacturing Practice
hgb	Hemoglobin
hct	Hematocrit
ICF	Informed Consent Form
ICH	International Conference on Harmonisation
IFALD	Intestinal Failure-Associated Liver Disease
IND	Investigational New Drug
INR	International normalized ratio
IRB	Institutional Review Board
ITT	Intention-to-treat
IVLE	Intravenous Lipid Emulsion
MCT	Medium Chain Triglycerides
MedDRA	Medical Dictionary for Regulatory Affairs
PDF/A	Portable Document Format/A (Adobe Systems Inc.)
PN	Parenteral nutrition
PNAC	Parenteral Nutrition-Associated Cholestasis
PNALD	Parenteral Nutrition-Associated Liver Disease
PP	Per protocol
PREA	Pediatric Research Equity Act
Q	Quarter

**Clinical Study Protocol SMOF-028-CP4**  
**Smoflipid® (lipid injectable emulsion)**

---

RBC	Red blood cells
SAE	Serious adverse event
SAP	Statistical Analysis Plan
SOP	Standard operating procedure
SUSAR	Suspected unexpected serious adverse reaction
TG	Triglycerides
US	United States
WBC	White blood cells

## **4. Introduction**

### **4.1 Background**

Parenteral nutrition (PN) is a life-saving procedure enabling adequate nutritional substrates to be provided to a patient whenever the nutritional needs cannot be met with oral or enteral nutrition. Total PN provides amino acids, dextrose, lipids, electrolytes, vitamins, trace elements, and water. Within PN regimens, intravenous lipid emulsions (IVLEs) have two main functions: 1) to supply calorie-dense energy and 2) to provide essential fatty acids (Hamilton et al 2006, Krohn and Koletzko 2006, Mascioli et al 1996, Waitzberg et al 2006). Intravenous lipid emulsions have now routinely been used in PN for more than 50 years, since Intralipid® was first registered in Sweden in 1962. In the USA, Intralipid 20% was approved in 1975.

Smoflipid® was first approved in Sweden in 2004 and is currently available in more than 65 countries worldwide. The US Food and Drug Administration (FDA) approved Smoflipid for use in adults in July 2016.

Smoflipid has been developed to optimize the fatty acid profile of the IVLE used in PN, providing a mixture of essential and non-essential fatty acids, including n-3, n-6, and n-9 fatty acids. Smoflipid is a fixed physical mixture of 4 different oils: soybean oil (30%), medium-chain triglycerides (MCT) (30%), olive oil (25%), and fish oil (15%). Compared to pure soybean oil emulsions, Smoflipid has a reduced amount of n-6 fatty acid linoleic acid which is partially replaced by n-9 and n-3 fatty acids. Smoflipid contains 200 mg/L  $\alpha$ -tocopherol, which protects unsaturated fatty acids against lipid peroxidation. Furthermore, Smoflipid contains only approximately 30% of amount of phytosterols contained in Intralipid 20%.

The 2014 clinical guidelines of the American Society for Parenteral and Enteral Nutrition (A.S.P.E.N.) on support of pediatric patients with intestinal failure at risk of PNALD (Wales et al 2014) states that no recommendation can be made for use of a fat emulsion with soy oil, medium-chain triglycerides, olive oil, and fish oil (Smoflipid) until it is approved for use in the United States. In 2016, (A.S.P.E.N.) and the Society of Critical Care Medicine (SCCM) issued updated guidelines for nutrition support in critically ill adult patients, which have stated that alternative (oil-based) IVLEs may provide an outcome benefit over soy-based IVLEs, and should be considered in critically ill patients who require PN (McClave et al 2016).

Prolonged use of PN in the setting of long-term intestinal failure has been associated with hepatic complications reflected by elevated bilirubin levels after approximately 2 to 3 weeks of PN (Christensen et al 2007). In this context, elevated bilirubin levels are considered to be a marker for evolving PN-associated cholestasis (PNAC) which can lead to PN-associated liver disease (PNALD) (Colomb et al 2000, Javid et al 2011, Koseesirikul et al 2012, Pichler et al

---

 In this study protocol, the terms PNAC and PNALD are used synonymously and are defined by direct bilirubin levels > 2 mg/dL.

## **Clinical Study Protocol SMOF-028-CP4 Smoflipid® (lipid injectable emulsion)**

---

2012). Parenteral nutrition-associated liver disease is considered to be multifactorial, and various aspects of PN may promote cholestasis (Wales et al 2014). In recent years, investigators focused on the role of the soybean oil-based IVLEs in the development of PNALD due to their high content of the  $\omega$ 6 fatty acid linoleic acid (C18:2 $\omega$ 6, 52% to 54% in Intralipid) and plant sterols (phytosterols) and their low content of  $\alpha$ -tocopherol (Burrin et al 2014, Clayton et al 1998, Ng et al 2015, Wales et al 2014).

Three company-sponsored studies comparing Smoflipid to Intralipid 20% in the pediatric population were completed in 2005 and 2006. The studies included preterm neonates, infants, and children up to 11 years of age (Goulet et al 2010, Rayyan et al 2012, Tomsits et al 2010). The data from these studies showed that the use of Smoflipid was safe and effective. A beneficial effect on liver parameters was found, although liver function was not the primary endpoint in these studies. In two studies, significantly greater decreases from baseline values were seen in total and direct bilirubin in the Smoflipid versus Intralipid 20% group (Goulet et al 2010, Rayyan et al 2012). In the third study, lower gamma-glutamyl transferase levels were noted in the Smoflipid group versus the Intralipid 20% group (Tomsits et al 2010). In these studies, PN was administered for up to 2 weeks or for up to 4 weeks.

Another company-sponsored study in the pediatric population was started in December 2015 in the USA and is currently ongoing. This prospective, randomized, controlled, double-blind, parallel-group trial compares safety and efficacy of Smoflipid to Intralipid 20% in hospitalized neonates and infants requiring at least 28 days of PN. The targeted maximal lipid dose is 3.0 g/kg/day. The primary objective of the study is to show the superiority in safety of Smoflipid over Intralipid 20% as measured by the number of patients in each treatment group who develop conjugated bilirubin > 2 mg/dL during the first 28 days of study treatment. This ongoing US Smoflipid study, and the study outlined in this clinical study protocol, will provide a substantial database for the short-term and long-term pediatric use of Smoflipid in the USA.

### **4.2 Rationale and Purpose of the Study**

Smoflipid was approved by the FDA for use in adult patients in July 2016. As required by section 505B(a) of the US Federal Food, Drug, and Cosmetic Act (FDCA), the safety and effectiveness of the new product for the claimed indications in pediatric patients must be assessed. For this reason, Fresenius Kabi will conduct this postmarketing study in pediatric patients 3 months to 16 years of age.

The present protocol describes a prospective, randomized, double-blind, parallel-group, active-controlled, multicenter study to evaluate the safety and efficacy of Smoflipid administered for at least 90 days, and continued for all patients who remain on PN for up to 1 year, compared to standard of care soybean oil based lipid emulsion (Intralipid 20%) administered for the same duration. Per the request of the FDA, the study's efficacy assessments will include anthropometric measures and evaluation of the risk of developing essential fatty acid deficiency (EFAD). Genetic polymorphisms in the fatty acid desaturase genes (FADS) FADS1 and FADS 2 should be determined in at least a subset of patients. The study's safety assessments will include evaluation of the risk of developing PNALD/PNAC. Plasma

## Clinical Study Protocol SMOF-028-CP4 Smoflipid® (lipid injectable emulsion)

---

phytosterol levels will be included as well.

### 4.3 Benefit/Risk Assessment

Parenteral nutrition is a lifesaving treatment if oral or enteral intake is impossible or not sufficient for a prolonged time. In this study only patients with indication for long-term PN suffering from reversible or irreversible intestinal failure will be included, e.g., patients with short bowel syndrome, intestinal atresia, abdominal surgical procedures due to gastroschisis or omphalocele closure, necrotizing enterocolitis, gastrointestinal motility disorder, or mucosal enteropathy.

Patients will receive the study drugs as part of their PN support for at least 90 days either during their hospitalization or in the home care setting. It is standard clinical practice to incorporate lipid emulsions into the PN protocol to ensure an adequate supply of essential fatty acids and energy. It is not possible to supply these calories with dextrose alone, because the excess dextrose intake that would be required is associated with metabolic complications and liver damage (Koletzko et al 2005).

Both study drugs, Smoflipid and Intralipid 20%, are approved in more than 60 countries for both adult and pediatric populations. In the USA, the comparator drug Intralipid 20% has been approved since 1975 for adult and pediatric use. Smoflipid was approved by the FDA for use in adults in July 2016. The present pediatric study is requested by the FDA as a post-marketing requirement for Smoflipid.

According to the latest “Periodic Safety Update Report” for Smoflipid, approx. 1.0 million patients were treated with Smoflipid from February 2015 to January 2018. Approx. 2.2 million patients received Smoflipid since the first registration in February 2004.

According to the latest “Periodic Safety Update Report” for Intralipid 10%, 20%, 30%, approx. 4,159,000 patients have received Intralipid 20% from March 2014 to September 2018. Since July 1999 approx. 10 million patients have received Intralipid 20%.

During these reporting intervals of both drugs, no actions have been taken or have been proposed for safety reasons. Based on the available safety data for Intralipid 20% and Smoflipid no change of the risk-benefit ratio of both products was identified. For both drugs the risk benefit balance was stated to remain positive.

According to the Smoflipid Prescribing Information ([Appendix 1](#)), the adverse reactions in > 1% of 229 patients treated in clinical studies with Smoflipid were nausea (9%), vomiting (7%), hyperglycemia (5%), flatulence, pyrexia, abdominal pain (4% each), increased blood triglycerides, hypertension (3% each), sepsis, dyspepsia, urinary tract infection, anemia, and device related infection (2% each). Furthermore, the components of Smoflipid may cause hypersensitivity reactions. Parenterally administered lipid emulsions are an independent risk factor for the development of catheter-related bloodstream infections.

According to the Prescribing Information of the standard-of-care emulsion Intralipid 20%

---

## Clinical Study Protocol SMOF-028-CP4 Smoflipid® (lipid injectable emulsion)

---

(Appendix 2), the most frequent adverse reactions are inseparable from the PN procedure with or without Intralipid 20%; these are adverse reactions due either to contamination of the I.V. catheter or to vein irritation by concurrently infused hypertonic solutions. Immediate or early adverse reactions more directly related to Intralipid 20% reported to occur in an incidence of <1% in clinical trials are dyspnea, cyanosis, allergic reaction, hyperlipemia, hypercoagulability, nausea, vomiting, headache, flushing, increase in temperature, sweating, sleepiness, and others. Among delayed adverse reactions are hepatomegaly, jaundice due to central lobular cholestasis, splenomegaly, thrombocytopenia, leukopenia, and transient increases in liver function tests.

In general, it can be concluded that study patients treated with either Smoflipid or Intralipid 20% are not exposed to higher risk than patients who are not included in the study and would receive PN according to institutional policy. In fact, study patients might even benefit from participating in the study as they will be more intensively monitored than under standard medical care.

## 5. Objectives

The objective of the study is to evaluate the safety and efficacy of Smoflipid compared to standard of care lipid emulsion Intralipid 20% administered via a central vein in pediatric patients 3 months to 16 years of age who require PN to meet their nutritional needs for at least 90 days and up to 1 year.

### 5.1 Study Hypothesis

The study hypothesis is that Smoflipid is safe and effective in pediatric patients when administered for 90 days or up to 1 year.

### 5.2 Target Variables

#### Efficacy variables:

- Body weight (weight velocity as z-score change from baseline).
- Body length/height (growth velocity as z-score change from baseline).
- Head circumference for patients who are < 36 months of age (z-score change from baseline).
- Fatty acid profiles including linoleic acid,  $\alpha$ -linolenic acid, arachidonic acid, docosahexaenoic acid, eicosapentaenoic acid, and Mead acid in total plasma (according to Mayo Medical Laboratories standards) and in red blood cell membranes.
- Triene/tetraene ratio (Holman Index) in plasma to assess essential fatty acid deficiency (EFAD). Severity of EFAD will be graded based on triene/tetraene ratio, as suspected  $\geq 0.05$ , moderate  $\geq 0.20$  and severe  $\geq 0.40$  (Cober et al 2012).

## Clinical Study Protocol SMOF-028-CP4 Smoflipid® (lipid injectable emulsion)

---

### Safety variables:

- Incidence of PNALD/PNAC: Number of patients in each treatment group with direct bilirubin levels > 2 mg/dL, confirmed by a second sample collected 7 days after the first sample (incidence of PNALD/PNAC). Time from Study Day 1 until reaching direct bilirubin levels > 2 mg/dL, followed up by a second sample collected 7 days after the first sample (time of developing PNALD/PNAC). (i.e., presented as the Study Day on which for the first time the direct bilirubin level was found > 2 mg/dL.)
- Sterols in plasma including phytosterols:  $\beta$ -sitosterol, campesterol, stigmasterol, brassicasterol, ergosterol, cholesterol, desmosterol, lanosterol,  $\beta$ -sitostanol, lathosterol, squalene (a sterol precursor).
- Laboratory values: (blood, plasma, or serum): triglycerides, direct bilirubin, total bilirubin, alanine aminotransferase (ALT), aspartate aminotransferase (AST), gamma-glutamyl transferase (GGT), alkaline phosphatase (ALP), creatinine, urea nitrogen, electrolytes (Na, K, Mg, Cl, Ca, Phosphate), trace elements (ferritin, Zn, Se, Cu, Mn, Cr), glucose, total protein, C-reactive protein (CRP), white blood cells (WBC), red blood cells (RBC), and platelet counts, hemoglobin (hgb), hematocrit (hct), international normalized ratio (INR).
- Vital signs: blood pressure, heart rate, body temperature.
- All adverse events (AEs).
- The relation between genetic polymorphisms in the fatty acid desaturase genes FADS1 and FADS2 and plasma concentrations of linoleic acid,  $\alpha$ -linolenic acid, arachidonic acid, docosahexaenoic acid, eicosapentaenoic acid, and Mead acid, as well as relation to EFAD (triene/tetraene ratio).

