### Serum triglycerides for intravenous lipid dose management:

#### A) Patients who start PN:

During dose titration, levels of TG will be monitored daily. Should TG exceed 250 mg/dL, the study drug will be held until analysis of another blood sample on the following morning. If TG are  $\leq$  250 mg/dL the study drug is restarted. If not this procedure has to be repeated on each subsequent morning. If after 3 days TGs still exceed 250 mg/dL, the patient will be removed from the study.

Once the target dose has been reached at level of serum TG  $\leq$  250 mg/dL, TG will be assessed monthly.

B) Patients who already receive PN:

Triglycerides levels will be monitored monthly. Should TG exceed 250 mg/dL, a confirmatory analysis must be performed after 7 days. If the confirmatory analysis reveals that TG still exceed 250 mg/L, the study drug dosage should be reduced, or the patient should be removed from the study, at discretion of the Investigator.

Direct bilirubin for intravenous lipid dose management:

Direct bilirubin levels will be assessed monthly. If at any point direct bilirubin exceeds 2.0 mg/dL (> 2.0 mg/dL), a confirmatory analysis must be performed after 7 days. If the confirmatory analysis reveals that direct bilirubin is still > 2.0 mg/dL, the lipid dose has to be decreased to 1 g/kg/day; dextrose dose should be increased accordingly to maintain adequate energy provision. Lipid dose will be maintained at 1 g/kg/d and not be increased again even if direct bilirubin levels decrease again to 2.0 mg/dL or lower.

If at any point direct bilirubin exceeds 4 mg/dL (> 4 mg/dL), the patient must be taken off study treatment. In this case, further PN treatment is at the discretion of the Investigator.

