#### Safety:

- Incidence of PNALD/PNAC: Number of patients in each treatment group with direct bilirubin levels > 2 mg/dL, confirmed by a second sample collected 7 days after the first sample (incidence of PNALD/PNAC).
- Time from Study Day 1 until reaching direct bilirubin levels > 2 mg/dL, followed up by a second sample collected 7 days after the first sample (time until developing PNALD/PNAC).
- Sterols in plasma including phytosterols:  $\beta$ -sitosterol, campesterol, stigmasterol, brassicasterol, ergosterol, cholesterol, desmosterol, lanosterol,  $\beta$ -sitostanol, lathosterol, squalene (a sterol precursor).
- Laboratory values (blood, plasma, or serum): triglycerides, direct bilirubin, total bilirubin, alanine aminotransferase (ALT), aspartate aminotransferase (AST), gamma-glutamyl transferase (GGT), alkaline phosphatase (ALP), creatinine, urea nitrogen, electrolytes (Na, K, Mg, Cl, Ca, Phosphate), trace elements (ferritin, Zn, Se, Cu, Mn, Cr), glucose, total protein, C-reactive protein (CRP), white blood cells (WBC), red blood cells (RBC), and platelet counts, hemoglobin (hgb), hematocrit (hct), international normalized ratio (INR).
- Vital signs: blood pressure, heart rate, body temperature.
- All adverse events (AEs).
- The relation between genetic polymorphisms in the fatty acid desaturase genes FADS1 and FADS2 and plasma concentrations of linoleic acid,  $\alpha$ -linolenic acid, arachidonic acid, docosahexaenoic acid, eicosapentaenoic acid, and Mead acid, as well as relation to EFAD (triene/tetraene ratio).

---

 In this study protocol, the terms PNAC and PNALD are used synonymously and are defined by direct bilirubin levels > 2 mg/dL.

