**Table 1: Study Schedule of Assessments and Procedures**

Assessments/ Procedures	Study Days	Screening / Baseline Visit Prior to Start of PN with Study Drugs	Treatment Phase Study Drug Administration Day 1 to Day 365 §			Final Study Visit / After End of Last Study PN
		Day 1 or Day -1 *	Day 1 Visit *	Weekly Call (± 1 day)	Monthly Visit (± 5 days)	Every 3 months, (during a monthly visit)
Informed consent		X				
Inclusion/exclusion criteria		X				
Demographics incl. race and ethnicity		X				
Pregnancy test, if applicable		X				
Randomization		X				
Medical history, demographic data		X				
Prior/concomitant medication		X			X	X
Body weight, length/height, head circumference		X			X	X
Physical examination incl. Tanner stage		X			X	X
Vital signs a		X			X	X
Blood sampling for standard laboratory b		X			X	X
Blood sampling for special laboratory c		X			X	X
Blood sampling for trace element analysis d		X				X
Start of study drug infusion			X			
Prior / concomitant nutrition e		X		X		X
Adverse events f		X	X	X	X	X
Blood sampling for genetic analysis (FADS1, FADS2) g					(X)	

\* Screening, baseline assessments and randomization are performed on Day 1, prior to the start infusion of study PN, or alternatively on Day -1, i.e., the day before Day 1. Study drug infusion starts on Day 1.

\*\* One day after last day of study drug administration.

§ During the treatment phase, study drug will be administered 5 to 7 days per week. A break of 1 or 2 days per week is allowed and will not lead to prolongation of the treatment phase.

a Blood pressure, heart rate, body temperature.

b Triglycerides, direct bilirubin, total bilirubin, ALT, AST, GGT, ALP, creatinine, urea nitrogen, electrolytes (Na, K, Mg, Cl, Ca, Phosphate), glucose, total protein, CRP, WBC, RBC, and platelet counts, hgb, hct, INR.

c Fatty acid profiles (linoleic acid,  $\alpha$ -linolenic acid, arachidonic acid, docosahexaenoic acid, eicosapentaenoic acid and Mead acid, analyzed in total plasma, and in red blood cell membranes);

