## **Clinical Study Protocol SMOF-028-CP4 Smoflipid® (lipid injectable emulsion)**

---

one month. If PN is still indicated after termination of the study treatment, it will continue per normal institution policy. Study drugs will no longer be used.

Between study Day 91 and Study Day 365, the study treatment will be terminated (i.e., late termination of study treatment) as soon as nutritional needs can be fully covered from enteral or oral nutrition, or is continued without a lipid emulsion (i.e., PN, or at least the lipid emulsion, is no longer indicated).

Whenever a patient has received his/her last dose of study drug, a Final Study Visit will be performed the following day to perform the end-of-study procedures. If after the last dose of study medication PN is still indicated, it will continue per normal institution policy.

To ensure safety of the patients during their study participation, medical monitoring will be performed on all safety relevant information collected during the trial. A medical safety officer will be available for safety related questions throughout the study.

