#### Direct bilirubin for intravenous lipid dose management:

Direct bilirubin levels will be assessed monthly. If at any point direct bilirubin exceeds 2.0 mg/dL (> 2.0 mg/dL), a confirmatory analysis must be performed after 7 days. If the

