## Clinical Study Protocol SMOF-028-CP4 Smoflipid® (lipid injectable emulsion)

---

confirmatory analysis reveals that direct bilirubin is still > 2.0 mg/dL the lipid dose has to be decreased to 1 g/kg/day immediately; dextrose dose should be increased accordingly to maintain adequate energy provision. Lipid dose will be maintained at 1 g/kg/d and not be increased again even if direct bilirubin levels decrease again to 2.0 mg/dL or lower).

If at any point direct bilirubin exceeds 4 mg/dL (> 4 mg/dL), the patient has to be taken off study treatment. In this case, further PN treatment is at the discretion of the Investigator.

For each Study Day, the prescribed dose, the dose actually infused, and the infusion time of study drug administration will be recorded in the eCRF.

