## **Clinical Study Protocol SMOF-028-CP4**

### **Smoflipid® (lipid injectable emulsion)**

---

treatment can last up to 365 consecutive days, i.e., for one year after randomization. No patient will receive study medication beyond Study Day 366.

Up to Study Day 90, study treatment will be terminated if enteral food tolerance increases and in consequence, if less than 60% of the patient's caloric requirements are provided by PN for at least one week (see 9.4 Exclusion after Study Admission).

After Study Day 90 the study treatment will be terminated as soon as nutritional needs can be fully covered from enteral or oral nutrition or PN is continued without a lipid emulsion (i.e., PN, or at least the lipid emulsion, is no longer indicated).

The study will be terminated at any time, if infusion of the lipid emulsion cannot be continued because TG or direct bilirubin levels remain above the defined limits (cf. 10.3.4) after reduction of the study drug dosage.

During Final Study Visit, the same procedures will be executed as in the monthly Treatment Phase Visits (see above, 11.2.3). Additionally, the reason for study termination will be recorded if it takes place before Study Day 365.

**Note:** Should the Final Study Visit be performed between Day 90 and Day 365 and less than 1 week after the collection of the last blood samples, then the blood sampling will not be repeated at the Final Study Visit.

If a patient is withdrawn from the study at any time due to an AE, the patient should be followed until an outcome of the AE can be defined.

In case the study participation is terminated because of withdrawal of the informed consent, the Final Study Visit, or single procedures of this visit, will only be executed if allowed by the patient's parent(s) or legal representative(s).

If the termination occurs before Study Day 365 because of cessation of PN, and PN is restarted later, a re-treatment with study drug is not allowed.

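### Incident PNALD/PNAC is defined both with and without a 7-day confirmation, and the difference matters most when the first raised direct bilirubin is already above 4 mg/dL

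*Combined protocol and SAP*

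**What the plan says.** **Incidence, with confirmation.** The Study outline (Target Variables, Safety) lists the outcome as "Number of patients in each treatment group with direct bilirubin levels > 2 mg/dL, confirmed by a second sample". Section 5.2 has the same rule: "confirmed by a second sample collected 7 days after the first sample".

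**Incidence, without confirmation.** The footnote attached to that bullet, which also appears in the outline and in 4.1, defines PNAC and PNALD by direct bilirubin above 2 mg/dL and mentions no repeat. The safety outcomes listed in 6.2 do the same.

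**Time to PNALD/PNAC.** Section 5.2 asks for a follow-up sample at 7 days but does not say that it has to confirm the first. It dates the event at the first value above 2 mg/dL.

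**Repeat and stopping rules (10.3.4).** "If at any point direct bilirubin exceeds 2.0 mg/dL (> 2.0 mg/dL), a confirmatory analysis must be performed after 7 days". Lipid is cut to 1 g/kg/day only if the repeat is still above 2.0 mg/dL. Separately: "If at any point direct bilirubin exceeds 4 mg/dL (> 4 mg/dL), the patient has to be taken off study treatment". The outline has the same stopping rule. Further PN is then at the investigator's discretion.

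**End of follow-up.** Section 6.1: "Whenever a patient has received his/her last dose of study drug, a Final Study Visit will be performed the following day". The Table 1 footnote agrees: "One day after last day of study drug administration". Section 12.3.6 ends the observation period at the Final Study Visit. Under the Note in 11.2.4, if that visit falls between Day 90 and Day 365 and the last blood sample is less than a week old, "then the blood sampling will not be repeated at the Final Study Visit".

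**The concern.** An incidence count needs one case rule, and here there are two. They differ for any value above 2 mg/dL that lacks a confirming repeat. For a first value between 2 and 4 mg/dL the conflict is mild: the bilirubin rules keep the patient on study drug and under observation while the repeat is drawn. For a first value above 4 mg/dL the protocol acts at once, so the repeat falls due when the patient has left study drug and has no further scheduled visit.

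These are the patients with the steepest rise. Whether one of them counts as a case could depend on which section the programmer follows, and on whether a sample was obtained after the patient left the study. PNALD/PNAC is the first-listed safety variable, and evaluating its risk is part of the rationale in 4.2 and 6.2, so the rule should not be open to choice.

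**Working it through.** **Inputs.** Direct bilirubin of 2.0 mg/dL or more excludes at entry (9.3). Samples are monthly, 30 ± 5 days (11.2.3). Planned size is 24 per arm in each age group (7.2.1), with a stated minimum of 23. The protocol gives no PNALD/PNAC rate, power or margin. Its own figure reproduces: 3 age groups × 2 arms × 24 = 144, so 72 per arm.

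**1. Timing.** Put the sample above 4 mg/dL on day 0 and the last dose on day t. The Final Study Visit is day t + 1 and the repeat is due on day 7. The documents do not give the delay t; I take 0 to 3 days.

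| t | Final Study Visit | Repeat after visit, 7 − (t + 1) | Repeat after last dose, 7 − t |
|---|---|---|---|
| 0 | day 1 | 6 days | 7 days |
| 1 | day 2 | 5 days | 6 days |
| 2 | day 3 | 4 days | 5 days |
| 3 | day 4 | 3 days | 4 days |

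Throughout this range the repeat comes after the last visit and off study drug. Before Day 90 the Final Study Visit does draw blood, but on day 1 to 4, too early to be the 7-day sample. Between Day 90 and Day 365 its routine draw is skipped.

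**2. How the same patient is classified.** First value above 2 mg/dL is already above 4 mg/dL:

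| 7-day repeat | Incidence, 5.2 and outline | Incidence, footnote and 6.2 | Time variable, 5.2 |
|---|---|---|---|
| above 2 mg/dL | case | case | onset day |
| not obtained | not a case | case | unclear |
| 2 mg/dL or lower | not a case | case | onset day |

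In the last row, and arguably the middle one, a patient can have an onset day without being an incident case.

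**3. Who is affected.** Only a patient who goes from 2 mg/dL or lower to above 4 mg/dL between consecutive samples. If the visit window runs from the previous visit, that is a mean rise of more than 2/35 = 0.06 to 2/25 = 0.08 mg/dL per day. A patient already confirmed above 2 mg/dL, or whose 7-day repeat is itself above 4 mg/dL, is counted either way. A first value above 2 mg/dL in a patient's last sample has a similar scheduling gap.

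**4. What an off-drug disconfirmation would need.** A fall from above 4 to 2 mg/dL or lower in 7 days is more than 2/7 = 0.29 mg/dL per day. That is 3.6 to 5 times the minimum rate of rise in step 3 (0.286/0.080 and 0.286/0.057).

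**5. Size.** One uncounted patient moves incidence by 1/72 = 1.4 points in an arm, 1/24 = 4.2 in an age-cohort arm, or 1/23 = 4.3 at the minimum. Assumed true incidences of 5%, 10% and 20% give 3.6, 7.2 and 14.4 cases in 72, rounded to 4, 7 and 14. Losing one case then cuts the arm's count by 25%, 14% and 7% (5.6% to 4.2%, 9.7% to 8.3%, 19.4% to 18.1%).

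A wider assumed range is 5% to 15% incidence, 10% to 50% of cases first seen above 4 mg/dL, and 50% to 100% of those unconfirmed. It gives from 72 × 0.05 × 0.10 × 0.50 = 0.2 to 72 × 0.15 × 0.50 × 1.00 = 5.4 uncounted cases per arm. The upper figure takes every input at its extreme, and nothing in the documents says where in this range the trial would lie.

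**The case against.** A reader might infer that the protocol discards its worst liver cases. The documents do not support that, for these reasons:

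- **The case is not always lost.** Under the footnote and 6.2 the patient is counted. The defect is two competing definitions, not one rule that always excludes.
- **The repeat is not cancelled.** The 10.3.4 rule applies at any point and so covers values above 4 mg/dL. The 11.2.4 Note drops routine sampling at one visit, not a repeat due under 10.3.4.
- **An unscheduled repeat is not peculiar to these patients.** Table 1 schedules none for anyone; every confirmation is triggered by a result. Section 11.3.2 provides for blood drawn at home and sent to the site, although the outline says all samples are taken at the monthly hospital visit. What is particular here is that the repeat falls after the last visit and off study drug.
- **Disconfirmation off drug is not shown to be likely.** The documents give no bilirubin kinetics that support the fall in step 4. A value that halves in a week may also be the transient or spurious result that a confirmation rule exists to screen out.
- **Biased comparison is not shown.** No rate, arm difference or direction can be derived.
- **Other safeguards exist.** Section 7.2.3 allows a missing-data category and leaves missing values to the SAP, whose text I did not have. Direct bilirubin is also reported as a laboratory variable. Laboratory adverse events of grade 2 or higher are recorded regardless of clinical relevance (12.3.1, Table 3), and unresolved ones are followed (12.3.6). Stops before Day 91 under lipid dose management are counted as withdrawals and not replaced (7.3). A DSMB monitors safety (12.5).

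These arguments limit the size of the problem and stand. They do not say which definition governs, or how to classify a treatment-stopping value without a confirming repeat. Adverse-event follow-up fixes no day-7 sample, and a missing-data category cannot classify a repeat that exists but was drawn off study drug.

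**Conclusion.** The point holds as an inconsistency in the case definition with one practical consequence. Under the 5.2 wording, a patient taken off study drug on a first value above 4 mg/dL may go uncounted, mainly because the repeat is not obtained. Reversal by an off-drug fall is possible but not shown to be likely. The time variable can disagree with the incidence count for the same patient.

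Impact is low. The study is descriptive with no primary outcome (7.2.1), the affected group is a narrow subset of unknown size, and no direction of bias is claimed. The per-patient effect of 1.4 or 4.2 points follows from the planned numbers; the incidences and shares in step 5 are assumptions. The timing conclusion assumes study drug stops within 3 days of the sample. The SAP could settle part of this.

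**What to change.** In 5.2, the Study outline and 6.2, define a case as either (i) direct bilirubin above 2 mg/dL confirmed at 7 days, or (ii) any value above 4 mg/dL that ends study treatment, with no confirmation needed. Align the footnote, and use the same rule for the time variable. Show patients with an unconfirmed value above 2 mg/dL in a separate row, and add a sensitivity count by arm of any value above 2 mg/dL. A sentence in the 11.2.4 Note that a repeat pending under 10.3.4 is still to be drawn would be a clarification only.

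The cost is wording, one table row and one sensitivity count, with no blood draw beyond the repeat already required. The downside is that a rare spurious value above 4 mg/dL would count as a case, although the protocol already stops treatment on such a value.
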